6.4 Criteria for Permanent Intervention Discontinuation for an Individual Participant

The criteria for permanent discontinuation of further study intervention for an individual participant are:

- Study product/intervention-related adverse event
- Reaching a defined clinical endpoint
- Completion of study intervention as defined in the protocol
- Request by participant to terminate study intervention
- Clinical conditions, which in the best judgment of the investigator are believed to be harmful or potentially life-threatening to the participant, even if not addressed in the AE Management section of the protocol

Participants may end their participation in the study at any time. No further data collection will occur from the date the decision is made to permanently discontinue the subject from the study. Participants who experience distress during the survey can access our list of community referrals, which can be viewed on our study's website, or contact the research staff using the information provided to the participant within the consent/assent process. Any unexpected adverse events will be immediately reported to the Columbia University IRB, if applicable. All study activities will halt pending Columbia University IRB review and recommendations if necessary. If a participant withdraws or is removed from the study, the site study coordinator will complete the necessary documentation regarding the participants off study status.

6.5 Criteria for Premature Study Discontinuation for an Individual Participant

The criteria for premature discontinuation from the study for an individual participant are:

- Lost to follow up as evidenced by failure by the participant to attend specified consecutive clinic visits, at the discretion of the site investigator;
- Participant repeatedly non-compliant with study intervention as prescribed;
- Request by participant to withdraw assent/consent;
- The study is cancelled by the NIH;
- The study is cancelled for other administrative reasons;

- The participant becomes incarcerated or placed in detention during the study;
- The participant reports an HIV positive diagnosis;
- Participant judged by the investigator to be at significant risk of failing to comply with the provisions of the protocol as to cause harm to self or seriously interfere with the validity of study results; or
- Death of the participant

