Randomization to Intervention and Control (Delayed Intervention) Arms. Using the randomization module in REDCap and the approach described below, there will be random or minimally biased assignment of subjects to study arms. We will use block randomization with randomly permuted blocks(56) to reduce opportunities for selection bias. The advantage of the permuted block design is that treatment assignment is pre-determined before the trial begins and then assignment remains static throughout the course of the trial(57). Blinding and random assignment will be maintained through continuous supervision by key members of the research team. All staff and participants will be kept blinded to outcome measurements during data collection(58). This technique will maintain complete randomness of the assignment of a subject to a group. Participants will be randomized based on the use of a password protected computer- generated random numbers at baseline to avoid the possibility of study staff subverting randomization as has been noted in previous studies(59). Following completion of the informed assent/consent and baseline assessment, participants will be randomly assigned to one of the two trial arms using the randomization module in REDCap(57). This will minimize the biased assignment of study subjects(60).

Intervention Delivery. If the study participant is randomized to the intervention arm, they will have access to the MyPEEPS Mobile App for the next three months. Participants randomized to the control (delayed intervention) arm will be given access to MyPEEPS Mobile at the 3-month study visit. Through our dashboard, we can monitor when participants login to MyPEEPS Mobile, time spent on each activity, and whether they are actively using the intervention or just logged in. Participants will have 3 months to complete the 4 MyPEEPS Mobile modules, which includes 25 embedded mobile activities (See [Table 3](#)).

Participants in the intervention group will be able to access the MyPEEPS intervention from baseline until the end of month 3 and the control arm (delayed intervention) will have access to the MyPEEPS App from months 4-6 (see [Figure 2](#)). **Overview of data collection time points.** We will conduct simultaneous assessments for both study arms at baseline, 3 months, and 6 months.

Intervention Arm	Baseline		Follow-Up		Follow-Up
	A	XXX	A	XXX	
Delayed Intervention Arm (Control)	A		A	XXX	A
TIMELINE	0 months		3 months		6 months

A =Assessment X =Intervention

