[Figure 2. Assessment Time Points and Intervention Delivery for Each Study Arm](#)

The delayed intervention design is essentially a cross-over design in which data are collected in parallel from both study arms through the primary endpoint - 3-months post-randomization ([Figure 2](#)). The arms are then crossed over, which has multiple benefits, including: 1) for ethical reasons per our experience with HIV prevention interventions with transgender populations, the delayed intervention group receives the potential benefit of the

intervention at the point of cross-over; 2) at the 6-month follow-up, it provides for a test of the durability of the intervention effect in the intervention group (i.e., 3-months post-intervention, pre-post); 3) it provides an additional secondary test of the intervention effect in the delayed intervention arm (pre-post); and 4) it provides additional time points (and power) in the intervention group to test moderators of the trajectory of sexual risk over time. We successfully used this study design in an NIH-funded R34 study(61).

MyPEEPS avatars represent “regular guys” like the study participants who will walk the participants through the curriculum. Following the selection of an avatar, the study participant will navigate through each of the study activities. Participants do not need to complete an activity in a single sitting but can stop and come back to complete the activities at any time during the time frame before the 3-month follow-up. Study staff will have access to a dashboard to monitor module completion. In addition, participants will receive weekly text messages and/or e-mails (participants will select) to remind them to complete the MyPEEPS module. If 2 weeks have passed and a participant has not completed any modules, then the app will send out notification reminders to remind them to complete their modules.

4.6 Specific Aim 3 Procedures.

Overview. Post-intervention, we will conduct individual, in-depth, semi-structured interviews with participants who completed the intervention.

Sample. We will purposively select participants to represent a diverse set of experiences (e.g., participants who completed App Use, high vs. low sexual activity). Although we will continue to recruit participants until reaching thematic saturation, we anticipate conducting about 20 interviews

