6.1 PARTICIPANT TRACKING & CLINICAL MANAGEMENT

6.2 Retention Efforts

Study staff will track retention, which will be reviewed weekly by the PIs. As has been successful in previous studies with this population, including the MyPEEPS Mobile efficacy trial, we will: 1) obtain, at baseline, participants' email addresses, phone numbers, social media handles, as well as the addresses and contact information of people participants believe could help us locate them in the future; 2) allow for any time of day, and all days of the week, for participants to complete online assessment visits; 3) provide participants with numerous methods for contacting study staff, including providing study phone numbers, email addresses, and social media handles and if agreed to by the participant, having them program our site numbers into their mobile phone during the enrollment visit; 4) routinely verify participants' locator information at every contact point; 5) if correspondence is returned indicating a participant no longer has a given email address, study staff will telephone to obtain their new email address; 6) if the phone number is disconnected, we will contact them via their social media accounts and/or individuals listed in participants' records; and 7) if participants are not responsive after 5 email correspondence attempts and/or have given permission to message them via phone number, we will attempt to make contact using participants' phone numbers using IRB-approved scripts. We will make every effort to maintain contact with participants, even if they move or discontinue the intervention, for those still willing to complete follow-up assessment visits. Given the older study population proposed in this trial, we are confident we will retain at least 80% of the study population for this study proposed in this trial, we are confident we will retain at least 80% of the study population for this study.

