7.3.2 Data Management and Data Quality

Columbia University will be responsible for computerized survey programming, data capture, management, and analysis. All study information will be identified through the Participant Identification Number (PID) on all forms and computerized files. Data files will be exported from the ACASI program and imported into the SPSS database for storage. Computer data files never have any identifying information and are encrypted prior to transfer between study sites. Data entered into the SPSS database will not include any identifying information. Only authorized users with a login name and password will be able to open the computerized survey, and only those with administrative privileges will be able to access data. The study research assistant (RA) will use a login name and password to gain access to the software to administer it to a participant, but they will have no ability to access the saved data. The database, data structure, and data quality will be routinely reviewed by [name], and the Data Manager will set up the database, check data quality, and prepare the data for use. The Multiple PIs will work closely to plan analyses for various purposes, including for hypothesis testing and manuscript development and reports. Data quality will be examined before statistical analyses are conducted, including examination of missing data,

assessment of distributional assumptions, and identification of outliers. In addition to data quality, the comparability between intervention and control groups will be carefully examined, including baseline balance and differential attritions at all waves of follow-up. While differences are not expected from the randomized design, it is prudent to plan for this contingency so that sufficient follow-up data and appropriate statistical methods can be used for intent-to-treat analyses. The psychometric properties of instruments will also be examined, as will the patterns of missing data.

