7.3.3 Data Monitoring

For the study, weekly reports for the sites will be created by the data manager to review relevant app engagement data, barriers with recruitment/enrollment and retention, urine sample collection, compliance with the protocol, and accuracy and completeness of the records. The investigative team will hold reoccurring conference calls, and these reports will be briefly reviewed by the team at these meetings. These regular reviews will ensure close communication between the research assistants, quickly identify missing data points, and ensure consistent management of any issues with the protocol between sites.

Data quality will be examined before statistical analyses are conducted, including examination of missing data, assessment of distributional assumptions, and identification of outliers. In addition to data quality, the comparability between intervention and control groups will be carefully examined, including baseline balance and differential attritions at all waves of follow-up. While differences are not expected from the randomized design, it is prudent to plan for this

contingency so that sufficient follow-up data and appropriate statistical methods can be used for intent-to-treat analyses.

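### Section 6.5 lets undefined non-compliance with the app end outcome follow-up, and before month 3 it can do so in the intervention arm only

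*Combined protocol and SAP*

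**What the plan says.** The protocol keeps two lists. Section 6.4 covers stopping the intervention; section 6.5 covers leaving the study. The second list includes "Participant repeatedly non-compliant with study intervention as prescribed". No number of lapses, period or completion level is attached to it. The consequence stands in section 6.4: "No further data collection will occur from the date the decision is made to permanently discontinue the subject from the study".

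Section 6.2 points the other way: "We will make every effort to maintain contact with participants, even if they move or discontinue the intervention", for those still willing to be assessed. Sections 7.3.2 and 7.3.3 plan for differential attrition so that "sufficient follow-up data and appropriate statistical methods can be used for intent-to-treat analyses".

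On timing, section 4.5 says: "Participants randomized to the control (delayed intervention) arm will be given access to MyPEEPS Mobile at the 3-month study visit". The primary endpoint is 3 months after randomisation (sections 4.5 and 7.2). Section 4.5 also lets participants work at their own pace: they "can stop and come back to complete the activities at any time during the time frame before the 3-month follow-up". It answers non-use with prompts: "If 2 weeks have passed and a participant has not completed any modules, then the app will send out notification reminders".

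Section 7.7 prorates missing scale items, treats data missing for reasons unrelated to the outcome as missing completely at random, names multiple imputation for baseline values, and compares estimates with and without it. Table 5 in section 7.6 sets a compliance target (80% of participants completing at least 75% of the content), but as a feasibility threshold for the group, not a rule for removing an individual.

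**The concern.** Someone who abandons the app but would still answer surveys falls under both section 6.2 (keep following) and section 6.5 (may be removed, with no further data). Which applies is left to an undefined judgement made after randomisation and linked to exposure to the intervention.

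The criterion is also one-sided for the main comparison. Controls have no app to neglect before month 3, so until the primary endpoint only the intervention arm can lose participants this way. If non-users benefit less, removing them moves the estimate from the effect of offering the app towards the effect in those who use it.

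The pilot is not powered for efficacy (section 7.6), so no significance test is at stake. What is at stake is the effect size: section 7.6 makes quantifying it an objective and will use it to size the next trial. The attrition checks in sections 7.3.2 and 7.3.3 would reveal such a loss but not correct it, and section 7.7 names imputation only for baseline values.

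**Working it through.** The conflict itself is textual, and the plan gives no figure to reproduce. The arithmetic below only illustrates size.

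**Inputs from the documents.** 80 participants, 40 per arm (7.2); assessments at 0, 3 and 6 months; Arm and INT coded as in Table 7; a random-intercept GLMM with log link, Poisson or negative binomial (7.6); RR 0.55, the example in 7.6.

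**Assumptions, not in the documents.** A share q of each arm are non-users; non-users gain nothing (RR 1); their baseline mean is r times that of users, with r = 1 or 2; random-intercept SD 0.8; user baseline mean 4. The model equation is not legible in the released text, so wave was entered as categorical. Covariates were left out.

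**Intent-to-treat target.** RR = [(1−q)×0.55 + q×r] / [(1−q) + q×r].
- q = 0.2, r = 1: (0.44 + 0.20)/1.00 = 0.64.
- q = 0.2, r = 2: (0.44 + 0.40)/1.20 = 0.70.

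**Large-sample simulation, Poisson counts.** RR from the three-wave model:

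| Setting | r = 1 | r = 2 |
|---|---|---|
| Full follow-up, q = 0.2 | 0.64 | 0.70 |
| (a) All intervention-arm non-users removed before month 3 | 0.58 | 0.59 |
| As (a), only half removed | 0.62 | 0.66 |
| (b) All intervention-arm non-users removed only after month 3 | 0.66 | 0.74 |

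With baseline and 3-month data only, (a) gives 0.55 / 0.53, while (b) leaves 0.64 / 0.70 unchanged.

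At q = 0.1 and 0.3 the targets are 0.60 and 0.69 (r = 1) or 0.63 and 0.76 (r = 2). Setting (a) gives 0.57 and 0.59, or 0.57 and 0.61. Setting (b) gives 0.61 and 0.71, or 0.65 and 0.82.

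**Against sampling error at n = 80** (8 of 40 non-users per arm). Shift = ln(RR under removal / RR with full follow-up) / SD of log RR with full follow-up.
- Poisson, (a), r = 1: ln(0.576/0.636)/0.160 = −0.099/0.160 ≈ −0.6 SD.
- Poisson, (a), r = 2: ln(0.581/0.697)/0.145 = −0.182/0.145 ≈ −1.25 SD.
- Poisson, (b): ln(0.660/0.636)/0.160 ≈ +0.2 SD, and ln(0.738/0.697)/0.145 ≈ +0.4 SD.
- Negative binomial counts and model, (a): one run with an assumed dispersion size of 2 gave SDs of 0.275 / 0.251 and shifts of −0.29 / −0.62 SD; another gave about −0.2 / −0.7 SD.

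**No true effect.** Setting (a) returns 1.01 (r = 1) and 0.98 (r = 2).

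**The case against.** Sections 6.4 and 6.5 do separate stopping the app from leaving the study, so 6.2 and 6.5 collide only where non-use is itself treated as grounds for leaving. That is right, and the conflict is confined to that case. The intent-to-treat text is a clause about a contingency, not a defined analysis set; the criterion works against that aim rather than breaching a specified analysis.

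The study procedures also make early removal unlikely. Modules may be finished at any point before month 3, non-use triggers reminders, and surveys go out automatically. Non-completion in the intervention arm is settled only when access ends, and removal then leaves the 3-month comparison untouched. This stands and limits the practical weight of setting (a), but the written rule does not exclude early removal.

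The mixed model can use incomplete follow-up under missing at random. True, but fitted to all observed visits it is the model that gave 0.58 / 0.59 under early removal: loss tied to non-use is not explained by the variables in it.

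A reader might infer that the rule manufactures an apparent benefit. A raw comparison of post-randomisation means suggests so: with 20% removed and twice the mean count in those removed, 1/(0.8 + 0.2×2) = 0.83 under no effect. That contrast ignores the baseline counts; the repeated-measures model gives 1.01 / 0.98.

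**Conclusion.** The concern holds as a conflict between sections 6.2, 6.4 and 6.5 that lets an undefined, exposure-related judgement end outcome data collection, in the intervention arm alone up to the primary endpoint. It should be corrected, but it is not a fatal flaw in a pilot.

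The size is conditional. With 20% non-users who gain nothing, early removal of all of them in the intervention arm moves 0.64 / 0.70 to about 0.58 / 0.59. At 80 participants that is about −0.6 to −1.25 SD with Poisson counts, and about −0.2 to −0.7 SD with the overdispersed counts that the plan also allows for. Later removal moves the pooled estimate slightly towards no effect. The documents give neither the non-user share, nor the benefit in non-users, nor their risk.

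The documents do not support three stronger readings: that the rule always exaggerates the effect (direction depends on timing), that it produces false positives, or that early removal is expected to be common.

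**What to change.** Reconcile sections 6.2, 6.4 and 6.5 so that non-use of the app does not by itself end outcome data collection. This has to cover two bullets in 6.5: the non-compliance bullet, and the later one on investigator-judged risk of not complying with the protocol, under which the same people could otherwise be removed. Possible wording: *Non-use of the app does not by itself end outcome follow-up. The 3- and 6-month surveys are sent to every randomised participant who has not withdrawn assent or consent, or left the study for a reason other than app non-use.* This concerns outcome data only and takes no view on when app use should stop. If the non-compliance term is kept, define it.

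As a secondary change, state in section 7.7 that all randomised participants are analysed with all observed visits. Extend the comparison with and without imputation to missing 3- and 6-month counts, with app use (already collected as paradata) in the imputation model, and add a missing-not-at-random scenario. App use in that model helps only if some non-users have observed outcomes, so the follow-up wording matters more.

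The cost is protocol and SAP wording plus a little more analysis. REDCap already sends the surveys automatically (section 4.5), so extra follow-up cost is negligible. The estimated effect may look smaller.

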b) **The MyPEEPS Mobile Trial (U01MD011279; MPIs: [name] and [name]).** Our current trial of 700 YMSM has shown promising preliminary results. First, we have successfully reached our recruitment goals. Second, we conducted an interim analysis for the purposes of report to our Data and Safety Monitoring Board and evaluated the preliminary outcomes in the first half (N=350) of our study sample from baseline to 3-month follow-up. Higher self-efficacy for HIV prevention behaviors ($p<.001$) and more recent HIV tests in the past 3 months ($p=0.02$) were reported by the intervention group compared to control. The number of condomless anal sex acts was lower among the intervention group for both insertive anal sex acts ($p=0.03$) and receptive anal sex acts ($p=0.0001$). These preliminary findings were reported to our Data and Safety Monitoring Board and are very promising for supporting the use of this intervention for reducing HIV risk behaviors in YTM. Finally, and of great relevance to this proposed study, over 800 YTM screened into our study because of their interest, sexual risk, and behavioral vulnerability but were ineligible based on birth sex criteria. We will use the list of transgender men who we screened as part of their larger efficacy trial, as part of our recruitment efforts for the proposed R34 study. Further, we published the findings from our formative work in several peer-reviewed publications and presentations(23-27).

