7.4 Adverse events

7.4.1 Adverse event assessment

We anticipate that the Data Safety and Monitoring Board will define study-specific serious adverse events (SAEs). While we do not anticipate any SAEs, we will suggest looking for imbalance among treatment arms with regard to the following criteria: safety and data security and study drop-out

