7.5.1 Procedures to Ensure Compliance with Monitoring Plan and Reporting Requirements

Biweekly reports for the sites will be created by the study statistician to review relevant app engagement data, barriers with recruitment/enrollment and retention, laboratory and medical records, compliance with the protocol, and accuracy and completeness of the records. The

investigative team will schedule biweekly conference calls, and these reports will be briefly reviewed by the team. These regular reviews will ensure close communication between the research assistants, quickly identify missing data points, and ensure consistent management of any issues with the protocol between sites.

7.6 Data Analysis Plan for Aim 2

Assessment of feasibility and acceptability of the intervention (Table 5). We have specified the following measures of feasibility and acceptability: Retention Rates, Compliance Rates, Dose, Eligibility Criteria, Recruitment and Enrollment, Missing Data, Study Measures(68-70).

Table 5. Measures of Feasibility and Acceptability of MyPEEPS Mobile for YTM

Constructs	Measures	Threshold (if applicable)
Retention Rates	-How many enrollees remain in the study? -Are they about the same in both arms?	At least 80% will remain in the study.
Compliance Rates	What is the completion rate of app sessions by participants?	At least 80% will have completed at least 75% of the intervention content.
Dose	Is the dose of the intervention e.g., number of sessions adequate (assessment of paradata).	Does the dose need to be adjusted?
Eligibility Criteria	Are eligibility criteria acceptable, or do they need modification because they are too stringent?	Eligibility rates (number of individuals eligible among those approached)
Recruitment and Enrollment	What is the pace of recruitment? Barriers to recruitment and enrollment	
 Rates of refusal (number of refusals vs. enrolled among those approached) Rates of no shows
Missing Data Measures	What is the extent and patterns of missing data? Length of time and burden to the respondents	The survey questions (Number and Type) may need to be adjusted

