8.6 Benefits

The potential benefits to an individual participant in the study are not known. The potential benefits of the study to others could be considerable. If our hypotheses are true, this study will

make a significant contribution towards improving HIV incidence in YTM. This study has not been designed for the direct benefit of its participants; however, there are a number of ways in which they may derive benefit, such as awareness of HIV status, increased access to HIV prevention tools (e.g., testing, PrEP) and HIV services, if a participant sero-converts. The proposed research will inform the delivery of HIV prevention messages. The knowledge gained will contribute to the body of knowledge regarding the use of health information technology for improving the lives of YTM at risk for HIV. The avoidance of HIV throughout study participation will be a significant personal benefit to participants.

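### A reported HIV diagnosis takes a randomised participant off study and ends their surveys: a small but avoidable, outcome-related gap in follow-up

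*Combined protocol and SAP*

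**What the plan says.** Section 6.5, on premature discontinuation from the study, includes "The participant reports an HIV positive diagnosis". Its list also names repeated non-compliance with the intervention, incarceration and investigator judgement. Section 6.4, which mainly concerns stopping the intervention, adds: "No further data collection will occur from the date the decision is made to permanently discontinue the subject from the study". Section 6.5 does not repeat that sentence, but the sentence speaks of leaving the study, which is the subject of 6.5.

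Section 6.2 promises: "We will make every effort to maintain contact with participants, even if they move or discontinue the intervention". It does not mention people taken off study. Section 8.3.1 provides counselling and referral after a reactive test and is silent on surveys. Section 7.7 plans multiple imputation for baseline values and names no method for surveys lost to removal.

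Section 7.3.2 wants baseline balance and differential attrition examined "so that sufficient follow-up data and appropriate statistical methods can be used for intent-to-treat analyses". Section 7.4.1 adds: "we will suggest looking for imbalance among treatment arms with regard to the following criteria: safety and data security and study drop-out". Table 5 asks of retention: "Are they about the same in both arms".

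The event is foreseen. Section 3.2.1 admits people of unknown HIV status, and 8.6 lists among possible benefits "awareness of HIV status, increased access to HIV prevention tools (e.g., testing, PrEP) and HIV services, if a participant sero-converts".

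**The concern.** HIV-positive status is an exclusion at entry (3.3). That could justify stopping a prevention app, but it is no reason to stop measuring someone already randomised, and no other reason is given. The protocol already separates stopping the intervention (6.4) from leaving the study (6.5), and this item sits on the second list.

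The loss is not random with respect to the primary outcome, since people who acquire HIV probably have more condomless receptive acts than average. It may also differ by arm, in either direction. If the app works, fewer app-arm participants become infected. If the app promotes testing, more existing infections come to light in that arm. Only the app arm sees the testing activities in Table 3 before month 3, and the interim data of the parent app trial showed "more recent HIV tests in the past 3 months" in its intervention group (1.4).

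At stake are a few survey waves from the people of most interest to an HIV-prevention trial, and a rule that would carry over into the efficacy trial whose methods Aim 2 is meant to refine.

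**Working it through.** The documents state no expected number of such removals and no bias figure, so there is nothing to reproduce. From the documents: 80 randomised, 40 per arm, surveys at 0, 3 and 6 months, retention of at least 80% (80 × 0.20 = up to 16 lost). Everything else below is assumed.

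**1. New infections.** Assume incidence I of 0.5 to 4 per 100 person-years. The chance of diagnosis by time T (in years) is p = 1 − exp(−I·T/100).

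| I | Expected among 80 by month 3 | Expected by month 6 | Chance of at least one by month 6 |
|---|---|---|---|
| 0.5 | 0.1 | 0.2 | 18% |
| 1 | 0.2 | 0.4 | 33% |
| 2 | 0.4 | 0.8 | 55% |
| 4 | 0.8 | 1.6 | 80% |

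**2. Effect on the rate ratio by this route.** If a fraction f of an arm is removed and those people have k times the mean count of the rest, then full mean / observed mean = 1 + f(k − 1). Suppose removals are 45% fewer in the app arm (borrowing the relative risk of 0.55 that 7.6 uses for illustration) and k is 3 to 5. Then full ratio / observed ratio = [1 + 0.55p(k − 1)] / [1 + p(k − 1)].

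- I = 0.5, k = 3, six months: p = 0.0025, factor 0.998.
- I = 4, k = 5, six months: p = 0.0198, factor 1.0436/1.0792 = 0.967.

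The observed ratio would therefore lie about 0 to 3% too close to 1.

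**3. Existing infections found by testing.** Let u be the undiagnosed share at entry and t the share of controls tested in three months. Take a testing ratio of 1.75 (the illustrative figure in 7.6), and suppose every diagnosis leads to removal before the month-3 survey.

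- At least one removal in the app arm: 1 − (1 − 1.75ut)^40. In the control arm: 1 − (1 − ut)^40.
- Expected arm gap: 40 × 0.75 × u × t.
- u = 0.5%, t = 10%: 3% and 2%, gap 0.015 people.
- u = 3.2%, t = 30%: 49% and 32%, gap 0.29 people.

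The 3.2% is the overall prevalence in 1.2. It is not an upper limit, because the same section reports 3.5% to 11.8% among transgender men with cisgender male partners. These prevalences include people already diagnosed. As a stress case, u = 11.8% and t = 30% gives a gap of 40 × 0.75 × 0.118 × 0.30 = 1.06 people. Taking t = 30% implies that 0.30 × 1.75 = 52.5% of the app arm is tested within three months, whereas 24 of 49 (49%) in the formative sample had ever been tested.

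**4. Effect in the planned model.** This was simulated as a negative binomial mixed model with arm, wave and intervention terms and a random intercept. There was no true effect and an assumed mean of 6 acts. Two settings were used (intercept SD 0.8 with size 1.0; 1.2 with 0.7), and losses came from the top fifth by person-level rate. Estimated ratio relative to full data:

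- one app-arm person lost after baseline: 0.99
- two lost: 0.97 to 0.98
- one lost in each arm: 1.00
- one losing month 6 only: 1.01 to 1.02

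The SD of the log rate ratio was 0.33 to 0.40. The shift per person is 0.011 to 0.018 on the log scale. Multiplied by the gap, this gives 0.015 × 0.011 = 0.0002 to 0.288 × 0.018 = 0.005, and in the stress case 1.06 × 0.018 = 0.019. Even the last is only about 6% of one SD (0.019/0.33). This shift runs opposite to that in step 2.

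**5. Timing.** HIV testing is self-reported at the surveys (Table 6). A diagnosis first reported at month 3 arrives with that survey's act count and loses only month 6; one first reported at month 6 loses nothing. The primary 3-month comparison loses data only when a diagnosis is reported between surveys. If half are first reported on the month-3 survey, the gaps in step 3 halve.

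**6. What the change recovers.** By step 1 it recovers follow-up for 0.2 to 1.6 people of 80, plus any existing infections found. One person is 1/16 of the loss already accepted.

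**The case against.** The strongest reply is that nothing in the pilot's result turns on this. The expected shift is negligible against sampling error, the plan disclaims power for efficacy, and up to 16 losses are already tolerated. That stands, and it is why this is an optional improvement.

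The rule can also be defended on substance. The target population is HIV-negative or of unknown status. After a diagnosis, act counts no longer measure risk of acquiring HIV, and outcomes such as the participant's own PrEP use change meaning. That stands as a reason for a separate sensitivity analysis, not for leaving the data uncollected.

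There is a burden as well. Section 4.5 allows up to five automated reminders per survey, and newly diagnosed participants may be minors enrolled without parental consent. So continued surveys should be offered, not pressed.

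Three stronger readings are tempting, and the documents support none of them:

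- That the rule materially biases the primary comparison. The documents give no incidence, testing rate or undiagnosed share, the assumed ranges give small shifts, and the two mechanisms pull in opposite directions.
- That keeping these surveys open would complete the intent-to-treat set. Other removals in 6.5 and ordinary attrition would remain.
- That a removed participant leaves the analysis. Section 7.6 analyses all 80 from baseline with a mixed model, so earlier waves still contribute; one or two waves are lost.

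**Conclusion.** The concern holds as a minor design point. Sections 6.5 and 6.4 together end data collection for a randomised participant because of an event related to the primary outcome, and nothing elsewhere restores those surveys. The planned attrition checks would show a loss by arm but not recover it. The expected effect on the rate ratio is about 0 to 3%, on assumed incidence, testing, undiagnosed share and relative act counts. These ranges illustrate the size and are not bounds. Reading the 6.4 sentence as governing 6.5 is an inference from its wording, though the natural one.

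Repeated non-compliance belongs beside it. Before month 3 only the app arm can fail to comply with the app, so that removal is tied to arm by construction and may well be the larger of the two.

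**What to change.** - Move the HIV-diagnosis item from 6.5 to the intervention-discontinuation list in 6.4. Do the same with repeated non-compliance, so that either stops the app and not the surveys.
- State that the 3- and 6-month surveys stay open to every randomised participant who still consents, and reconcile the remaining 6.5 items with that sentence. The 6.4 sentence ending data collection also needs narrowing, since it would otherwise sit directly under the moved items.
- Make continued surveys optional after a diagnosis, with the counselling and referral in 8.3.1 coming first.
- Analyse as randomised. If any diagnoses occur, add a sensitivity analysis without the act counts that follow them, and say how those counts are to be interpreted.

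The cost is protocol wording, ethics review of the change (with any consent wording it needs), and probably one or two extra surveys for the HIV-diagnosis item on the automated REDCap schedule. The non-compliance change may add more; the documents give no number. The downside is the altered meaning of act counts after a diagnosis. With so few cases expected, the sensitivity analysis may turn out to be empty.
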